Study Protocol

“Does Antrum Size Matter in Sleeve Gastrectomy?”

Study Protocol

“Does Antrum Size Matter in Sleeve Gastrectomy? ”

BACKGROUND

Laparoscopic sleeve gastrectomy (LSG) is currently the most frequent primary bariatric procedure performed worldwide. LSG is safe and effective in terms of excess weight loss. It is a powerful metabolic operation that activates significant hormonal pathways that lead to changes in eating behavior, glycemic control and intestinal functions. LSG can be a faster procedure for its technical aspects (any need for intestinal anastomosis, being limited to the stomach transection). The most frequent and sometimes dangerous complications are leaking, hemorrhage, splenic injury, stenosis and Gastroesophageal Reflux Disease (GERD)(1). Despite its established efficacy and safety, dispute still exists on optimal operative technique for LSG: bougie size, distance of resection margin from the pylorus, the shape of section at the gastroesophageal junction, staple line reinforcement and intraoperative leak testing are among the most controversial issues (2). Indeed, different Authors have adopted a resection distance from the pylorus between 2 and 6–7 cm with various reasons (3). In favor of resections more distant to the pylorus, Authors argue that it seems to improve gastric emptying, prevent distal stenosis and reduce intraluminal pressure, potentially leading to a lower incidence of fistula and/or reflux. On the other hand, resections close to the pylorus seems to reduce more the gastric distensibility and increase intragastric pressure, potentially leading to a better satiation with less oral intake (4, 5). However, only few studies have investigated the differences between these two approaches (3). Thus, the primary aim of this randomized monocentric study is to evaluate variations in percentage of excess weight loss (%EWL) at 1 and 2 years follow-up after LSG in subject with a gastric resection starting from 2 cm from the pylorus (wide antrectomy) compared to those with a gastric resection starting from 6 cm from the pylorus (small antrectomy). Secondary aim-points are represented by evaluation of differences in morbidity, mortality, tolerance to food, incidence of reflux symptoms and GERD Health-Related Quality-of-Life (GERD-HRQL) score between the two groups.

Material and Methods

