2.6 Statistical Analysis

Statistical analysis was performed using Graphpad Quick Calcs (GraphPad version 6.04 for Windows, GraphPad Software, La Jolla California USA). Baseline comparisons were performed using chi-square tests and T-tests. Continuous variables are expressed as mean \pm standard deviation (SD). Differences between preoperative and postoperative parameters were compared by Wilcoxon paired rank test. For all tests, a two-sided $p < 0.05$ was considered statistically significant.

Sample size

THIS IS A CONTROLLED RANDOMIZED STUDY OF BINARY NON-INFERIORITY OUTCOME IN PARALLEL GROUPS. IF THERE IS TRULY NO DIFFERENCE BETWEEN THE STANDARD AND EXPERIMENTAL TREATMENT, THEN 138 PATIENTS ARE REQUIRED TO BE 90% SURE THAT THE LOWER LIMIT OF A ONE-SIDED 95% CONFIDENCE INTERVAL (OR EQUIVALENTLY A 90% TWO-SIDED CONFIDENCE INTERVAL) WILL BE ABOVE THE NON-INFERIORITY LIMIT OF -10. SAMPLE SIZE WAS CALCULATED WITH SEALED ENVELOPE LTD. 2012.

Appendix 2

Chief Investigator: [name], PhD – UOC Chirurgia Generale – Ospedale A. Rizzoli –

Lacco ameno napoli. [contact]; cellulare: [name].

Results summarized in the table:

Table 1 :Preoperative demographics data

Table 2: Weight, Body mass index, and the percentage of excess body weight loss and the Percentage Total Weight loss of the two groups at follow-up 3-6-12-24-months

Table 3: GERD Health-Related Quality-of-Life (GERD-HRQL) Score preoperative and postoperative scores follow-up 3-6-12-24 months

Table 4: Endoscopy Preoperative and at 1 and 2 years follow-up into two Groups

Table 1 Preoperative demographics data

Patients	Total	Group A (n=75)	Group B(n=75)
Age	33.6 ± 14	32.2 ± 8	34.2 ± 9
Male	39%	35%	38%
Female	61%	63%	62%
Height	151.2 ± 22	150.1 ± 23	152.8 ± 33
Weight kg	121.9 ± 21.7	124.5 ± 26.7	125.3 ± 23.5
BMI	44.23 ± 6.32	43 ± 8 (40–57)	44 ± 4(40–55)
ASA(I-II)(%)	65%	64%	66%
ASA(III-IV)(%)	35%	36%	34%
T2MD(%)	12(8.%)	7(9.3%)	5(6.6%)
Chronic obstructive pulmonary disease(%)	7(4.6%)	2(2.6%)	3(4%)
Heart Ischemia	1	0	0
Hypertension(%)	95(63%)	55(73.3%)	40(53.4%)

BMI body mass index, %EWL percentage excess weight loss, %TWL percentage total weight loss, Type 2 Mellitus Diabetes (T2MD)

Table 2: Weight, Body mass index, and the percentage of excess body weight loss and the Percentage Total Weight loss of the two groups at follow-up

Patients	3 months follow-up		p	6 months follow-up		p	12 months follow-up		p	24 months follow-up		p
	145/150			141/150			136/150			131/150		

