	Group A (n=72)	Group B(n=73)	p>0.05	Group A(n=70)	Group B(n=71)	P<0.05	Group A(n=67)	Group B(n=69)	p	Group A(n=65)	Group B(n=66)	p>0.05
BMI	30.9 ± 5.32	34.7 ± 4.18	P<0.05	26.13 ± 7.32	31.06 ± 3.12	P<0.05	24.2 ± 3.4	27.5 ± 4.3	P<0.05	25.2 ± 4.4	26.2 ± 3.3	p>0.05
EBWL%	40.9 ± 8.1	31.60 ± 8.7	P<0.05	54.1 ± 11.3	48.20 ± 12.5	P<0.05	63.7 ± 14.1	59.6 ± 12.5	P<0.05	62.8 ± 13.1	61.6 ± 10.5	p>0.05

Results

Table 3 GERD Health-Related Quality-of-Life (GERD-HRQL) Score preoperative and postoperative scores

Patients	Preoperative 150/150		3 months follow-up 145/150		p >0.05	6 months follow-up 141/150		P <0.05	12 months follow-up 136/150		P <0.05	24 months follow-up 131/150		p >0.05
	Group A (n=75)	Group B (n=75)	Group A (n=72)	Group B (n=73)		Group A (n=70)	Group B (n=71)		Group A (n=67)	Group B (n=69)		Group A (n=65)	Group B (n=66)	
GERD HRQL Score<15			38(52.7%)	57(78%)	P <0.05	36(51.4%)	56(78.8%)	P <0.05	47(70.4%)	55(79.7%)	P <0.05	49(75.3%)	55(83.3%)	P <0.05
GERD HRQL Score >16<30	7(9.3%)	9(12%)	29(40%)	15(20.5%)	P <0.05	30(42.8%)	14(19.7%)	P <0.05	16(23.8%)	13(18.8%)	P >0.05	14(21.5%)	10(15.1%)	P >0.05
GERD HRQL Score >31	-	-	5(6.9%)	1(1.3%)	P <0.05	4(5.7%)	1(1.4%)	P <0.05	4(5.9%)	1(1.4%)	P <0.05	1(1.5%)	0	P <0.05
Significant Vomit	-	-	11(15,3%)	3(4.1%)	P <0.05	6(8.6%)	2(2.8%)	P <0.05	6(8.9%)	2(2.9%)	P <0.05	2(3.1%)	1(1.5%)	P <0.05
Intolerance to food	-	-	2(2.7%)	0	P <0.05	1(1.4%)	0	p >0.05	0	0	p >0.05	0	0	p >0.05

Table 4: Endoscopy Preoperative and at 1 and 2 years follow-up into two Groups

	Preoperative Patients 150		1 year follow-up Patients 108/150(72%)		2 years follow-up Patients 105/150(70%)	
	Group A 75	Group B 75	Group A 53	Group B 55	Group A 52	Group B 53
Esophagitis						
A	4(5.3%)	5(6.7%)	9(16.9%)	7(12.7%)	5(9.6%)	5(9.4%)
B	-	-	11(20.7%)	5(9%)	9(17.3%)	3(5.6%)
C	-	-	2(3.8%)	0	1(1.9%)	0
D	-	-				
Esophageal biopsy						
Metaplasia	-	-	0	0	0	0
Helicobacter Pylori	9(12%)	7(9.3%)				
Hiatal Hernia< 5 cm	1(1.3%)	2(2.7%)	-	-	-	-

Figure 1 Diagram of Patients eliability

Flow Diagram

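### The P<0.05 flag on 12-month %EWL does not follow from the printed figures (t-test p = 0.075), and 10 of the 15 P<0.05 flags in the body of Table 3 fail on their own counts

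*Combined protocol and SAP*

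**What the plan says.** The Background of the combined protocol and SAP gives the primary aim as to "evaluate variations in percentage of excess weight loss (%EWL) at 1 and 2 years follow-up after LSG". Section 2.6 (Statistical Analysis) sets the criterion: "For all tests, a two-sided $p < 0.05$ was considered statistically significant". On methods it says "Baseline comparisons were performed using chi-square tests and T-tests" and assigns a paired Wilcoxon test to change from before to after surgery. It names no test for comparing the groups at follow-up. It also says that ± denotes the SD.

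Table 2 gives 12-month %EWL, with 67 patients in Group A and 69 in Group B, as "63.7 ± 14.1 59.6 ± 12.5 P<0.05". The 24-month comparison is marked p>0.05.

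Table 3 covers three GERD-HRQL score bands, significant vomiting and food intolerance at four visits. Its body has 20 between-group flags: 15 marked P<0.05 and 5 marked above 0.05.

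Both tables also carry p entries in their header rows. Table 2's header for 3 months reads "Group A (n=72) Group B(n=73) p>0.05". In Table 3 the column headed "24 months follow-up 131/150" is marked p>0.05.

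**The concern.** The 12-month difference in %EWL is small relative to its SDs and group sizes, and 12 months is one of the two primary time points. If the flag is unsupported, the tables offer no significant primary result.

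Many flagged comparisons in Table 3 rest on a handful of events. These are the symptom harms, so their flags shape any conclusion on reflux and tolerance. The follow-up test is unnamed and header flags disagree with body flags, so a reader cannot tell what a flag means or check it.

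**Working it through.** **1. %EWL at 12 months (Table 2).** Inputs: 63.7, SD 14.1, n = 67; 59.6, SD 12.5, n = 69.

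- Difference = 63.7 − 59.6 = 4.1
- Pooled variance = (66 × 14.1² + 68 × 12.5²) / 134 = 177.2, so pooled SD = 13.31
- SE = 13.31 × √(1/67 + 1/69) = 2.283
- t = 4.1 / 2.283 = 1.80 on 134 df, two-sided p = 0.0748 (Welch: SE 2.287, p = 0.0754)
- 95% CI = 4.1 ± 1.978 × 2.283 = −0.42 to 8.62

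The printed P<0.05 is not reproduced. Variants:

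- Smallest difference giving p = 0.05 at these SDs and numbers: 1.978 × 2.283 = 4.52.
- Most favourable rounding (63.75, SD 14.05 against 59.55, SD 12.45): p = 0.067.
- All 75 per arm: SE = √((14.1² + 12.5²)/75) = 2.176, t = 1.88, p = 0.061.
- One-sided: p = 0.037, which the two-sided rule in section 2.6 excludes.

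**2. The other Table 2 body flags.** The same t-test agrees with all seven. %EWL: p<0.0001 at 3 months, 0.004 at 6, 0.56 at 24. BMI: p<0.0001 at 3, 6 and 12 months, 0.14 at 24.

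**3. Table 3.** Each cell is a 2×2 table. Worked example, vomiting at 12 months: 6/67 against 2/69, pooled proportion 8/136 = 0.0588, difference 0.0606, SE = √(0.0588 × 0.9412 × (1/67 + 1/69)) = 0.0404, z = 1.50, uncorrected chi-square p = 0.133.

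The ten cells marked P<0.05 that fail:

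| Row, visit | A | B | Chi-square p | Fisher p |
|---|---|---|---|---|
| Score <15, 12 mo | 47/67 | 55/69 | 0.198 | 0.237 |
| Score <15, 24 mo | 49/65 | 55/66 | 0.261 | 0.287 |
| Score >31, 3 mo | 5/72 | 1/73 | 0.092 | 0.116 |
| Score >31, 6 mo | 4/70 | 1/71 | 0.167 | 0.209 |
| Score >31, 12 mo | 4/67 | 1/69 | 0.161 | 0.205 |
| Score >31, 24 mo | 1/65 | 0/66 | 0.312 | 0.496 |
| Vomiting, 6 mo | 6/70 | 2/71 | 0.140 | 0.166 |
| Vomiting, 12 mo | 6/67 | 2/69 | 0.133 | 0.162 |
| Vomiting, 24 mo | 2/65 | 1/66 | 0.550 | 0.619 |
| Food intolerance, 3 mo | 2/72 | 0/73 | 0.152 | 0.245 |

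The five that reproduce (Fisher): score <15 at 3 and 6 months, 0.0016 and 0.0008; the middle band at 3 and 6 months, 0.012 and 0.004; vomiting at 3 months, 0.026. The split is also 10 of 15 under Yates, likelihood-ratio, unpooled Wald and Boschloo tests.

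**4. Cells that could not reach 0.05.** Fisher p for the most extreme split of the events seen:

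- 1 event (score >31, 24 months): 65/131 = 0.50
- 2 events (food intolerance, 3 months): (72 × 71)/(145 × 144) = 0.24
- 3 events (vomiting, 24 months): (65 × 64 × 63)/(131 × 130 × 129) = 0.12

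**5. Internal contradictions.** In Table 3, 1/65 against 0/66 is marked P<0.05, while 1/70 against 0/71 (food intolerance, 6 months) is marked p>0.05. Table 3's header marks 3 and 24 months p>0.05, but all five body rows at 3 months and three at 24 months say P<0.05. Table 2's header marks 3 months p>0.05, but both body rows say P<0.05.

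**The case against.** **Another test may have been used for %EWL.** This stands as a limit. Simulated data forced to the printed means and SDs (assumed shapes, 4,000 runs each) gave these Mann-Whitney p-values: median 0.084 for normal data (95% range 0.029 to 0.186), 0.084 for right-skewed (0.040 to 0.157) and 0.039 for left-skewed (0.013 to 0.107). The 12-month flag is therefore unsupported by what is printed, not shown to be false. Table 3 holds counts, so this defence does not reach it.

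**A one-sided reading explains the flag.** One-sided p is 0.037, and the sample-size paragraph does use a one-sided 95% interval. That belongs to the non-inferiority calculation; section 2.6 makes all tests two-sided. A one-sided chi-square would rescue only one more Table 3 flag (score >31 at 3 months, 0.046).

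**The flags are before/after tests.** There is one flag per pair of groups, and %EWL has no baseline value. A fall in mean BMI from 43 to 25.2 in Group A could hardly carry p>0.05 at 24 months.

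**Header flags may have been displaced in extraction.** That is possible, especially in Table 2, so they are weaker evidence. The body flags sit beside their own counts and do not depend on them.

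**Removing flags could hide harm.** Table 4 is untouched. Grade B alone reads "11(20.7%) 5(9%) 9(17.3%) 3(5.6". Adding grade C gives 13/53 against 5/55 at 1 year and 10/52 against 3/53 at 2 years (Fisher 0.040 and 0.042; Yates 0.058 and 0.070). The documents do not set this grouping as an endpoint, and endoscopy covers 108 and 105 of 150 patients, so it is exploratory.

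**Conclusion.** The concern holds. By t-test on the printed figures neither primary time point is significant (p = 0.075 at 12 months, 0.56 at 24), yet Table 2 flags the first. This assumes that ± is the SD, as section 2.6 says, and that the printed group sizes are the analysed numbers. What patient-level data would show under another test remains open.

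For Table 3 the conclusion is firm: 10 of 15 P<0.05 flags are unsupported, including 6 of 6 at 12 and 24 months, under every two-sided test tried. No consistent test explains the opposite flags on one event against none. This must be corrected before the tables are relied on.

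**What to change.** - In section 2.6, name one two-sided between-group test per outcome type, for example a t-test for %EWL and Fisher's exact test for sparse counts. Apply it at every visit and state that it was chosen after the data were seen.
- Recompute every between-group p-value in Tables 2 and 3 from patient data. Print exact values with differences and 95% CIs. Use 0.075 only as a check on the 12-month t-test.
- Replace unsupported flags, and define or delete the header-row flags.
- Do not describe 12-month %EWL or the 12- and 24-month Table 3 comparisons as significant unless the recomputation shows it. Consider Table 4 in any reflux conclusion, labelled exploratory where the grouping was unplanned.
- Reconcile smaller points that change no flag. Table 3's score bands differ from those under Pre-operative evaluation. At 24 months they sum to 49 + 14 + 1 = 64 of 65 and 55 + 10 + 0 = 65 of 66. Section 2.5 schedules vomiting and food intolerance at 6, 12 and 24 months, but Table 3 also tests them at 3.

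The cost is a few hours of re-analysis and an admission that the tests were chosen late. The effect cuts both ways: losing the %EWL flag weakens the claimed benefit in Group A, and losing the ten Table 3 flags weakens the claimed symptom harm in the same group.

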2.2 Study Design

The study is designed as a randomized controlled trial. Primary outcome was the evaluation of %EWL between 2 groups. Secondary outcomes were evaluation of morbidity, mortality, incidence of reflux symptoms and Quality of Life score between the Groups.From January 2015 to November 2017, a series of 218 consecutive patients suffering from morbid obesity and scheduled for LSG were included; informed consent was obtained from each participant before surgery.

Inclusion criteria were morbid obesity defined as BMI 40 kg/m² and age between 25–50 years old. Obesity-related comorbidities included Type 2 Mellitus Diabetes (T2MD), hypertension, hyperlipidemia, bronchial asthma, osteoarthritis and degenerative joint disease.

Exclusion criteria

Patients with previous bariatric surgical procedures, endocrine disorders causing obesity (as hypothyroidism and Cushing disease), pregnancy or lactation, psychiatric illness, or recent diagnosis of malignancy, inflammatory bowel disease, Barrett's esophagus, and GERD with esophagitis scored as or greater than grade B, a large hiatal hernia (>3 cm) were excluded from the study. In case of absence or grade A esophagitis, GERD was also considered as severe with GERD-HRQL > 30 and when interfering with daily activities or inducing dietary restriction despite, also these were excluded.

One hundred-fifty patients were considered eligible and randomized in two Group (Group A n = 75, Group B n=75). All patients underwent elective laparoscopic LSG. In the case of conversion to open surgery, patients were excluded. Details of enrollment procedure are shown in Fig. 1.

Randomization

Participants were randomly assigned to one of the two groups using computer-generated permuted blocks (www.randomization.com). Outpatient clinic controls were done by surgeons/surgical residents/GP blinded for the groups. Patients were randomized into 2 groups based on the distance to pylorus of resection: Group A (n=75) at 2 cm, Group B(n=75) at 6 cm. Results were obtained at 1 and 2 years follow-up. The randomization scheme was generated using the web site Randomization.com (<http://www.randomization.com>).

Blinding Process

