2.5 Post-operative evaluation

All patients were actively clinical followed up regularly at 3, 6, 12 and 24, included GERD-HRQL. UE was performed in all patients at 12 or 24 months. Significant vomiting and food intolerance were evaluated at 6, 12 and 24 months follow-up. Vomiting was considered significant when occurring at least three times a week and food intolerance was defined as vomiting occurring almost each day. Esophageal biopsies were performed only in case of esophagitis \geq B (9).

Weight loss parameters were recorded at 3, 6, 12 and 24 months after the LSG : BMI (in kg/m²), %EWL and percentage total weight loss %TWL from baseline. The secondary endpoints were GERD and esophagitis studied with Upper endoscopy and GERD score

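### The arms are compared at each visit only in patients seen at that visit, with no stated method for the 14 and 19 randomised patients missing from the 12- and 24-month %EWL comparisons

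*Combined protocol and SAP*

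**What the plan says.** Section 2.2 gives the randomised set: "One hundred-fifty patients were considered eligible and randomized in two Group (Group A n = 75, Group B n=75". The Background sets the primary aim, which is to "evaluate variations in percentage of excess weight loss (%EWL) at 1 and 2 years follow-up after LSG". Section 2.5 provides the repeated measurements: "Weight loss parameters were recorded at 3, 6, 12 and 24 months after the LSG".

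Table 3 heads its follow-up columns "3 months follow-up 145/150", "6 months follow-up 141/150", "12 months follow-up 136/150" and "24 months follow-up 131/150". Table 2 carries the same counts. By arm (A/B) they are 72/73, 70/71, 67/69 and 65/66, and each p-value belongs to one visit.

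Section 2.6 names chi-square and t-tests for baseline comparisons, a paired Wilcoxon test for change from before to after surgery, and a two-sided 0.05 threshold. It defines no analysis population, missing-data method or longitudinal model, and names no test for comparing the arms at follow-up. That the analysis uses attenders only is an inference from the denominators and from the absence of any other method.

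**The concern.** A patient who is not seen at 12 or 24 months contributes nothing to the primary comparison at that visit. Any weight recorded at 3 or 6 months counts only in the columns for those visits. An attender-only difference can be trusted when loss is unrelated to outcome, or when it shifts both arm means equally. Neither is assured here. At 3 months significant vomiting was 11/72 in A against 3/73 in B, and a GERD-HRQL score in the two upper bands was 34/72 (29 + 5) against 16/73 (15 + 1). Either could affect who returns. Similar numbers lost do not guarantee that similar patients were lost.

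At stake are how firmly the 12-month %EWL difference can be stated, and how much the 24-month reflux comparison can carry.

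**Working it through.** **Inputs.** Randomised 75/75 (section 2.2). %EWL, mean ± SD (Table 2): 12 months A 63.7 ± 14.1 (n=67), B 59.6 ± 12.5 (n=69); 24 months A 62.8 ± 13.1 (n=65), B 61.6 ± 10.5 (n=66). GERD-HRQL bands at 24 months (Table 3): A 49, 14, 1; B 55, 10, 0.

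**Missing patients.**
- 12 months: A 75 - 67 = 8, B 75 - 69 = 6; 14/150 = 9.3%.
- 24 months: A 75 - 65 = 10, B 75 - 66 = 9; 19/150 = 12.7%.
- Not seen at 3 months: A 3, B 2, total 5. So at least 14 - 5 = 9 of those missing at 12 months, and at least 19 - 5 = 14 of those missing at 24 months, have a 3-month weight. These lower bounds hold for any pattern of missed visits.

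**12-month comparison from the printed summaries.**
- Pooled SD = sqrt((66 × 14.1² + 68 × 12.5²)/134) = 13.31.
- SE = 13.31 × sqrt(1/67 + 1/69) = 2.28.
- Difference A - B = 4.1; t = 4.1/2.28 = 1.80; two-sided p = 0.075.
- 95% CI = 4.1 ± 1.978 × 2.28 = -0.4 to 8.6.

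Table 2 prints P<0.05. Halving the p-value gives 0.037, but section 2.6 specifies two-sided tests. A rank test cannot be checked from means and SDs.

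**Sensitivity at 12 months.** Hold the SE fixed and let B's lost patients resemble B's attenders. If A's 8 lost patients differ from A's attenders by s, the difference moves by s × 8/75. The lower limit reaches zero when s = (4.52 - 4.1)/(8/75), about 3.9 points, or 0.28 SD. A small shift is enough to change whether the result is significant.

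**Sensitivity at 24 months.**
- Difference 62.8 - 61.6 = 1.2; SE = sqrt(13.1²/65 + 10.5²/66) = 2.08; 95% CI -2.9 to 5.3; p = 0.56.
- On the same basis with 10/75, significance against A needs A's lost patients to average (1.2 + 4.1)/(10/75), about 40 points (3 SD), below A's attenders.
- Significance in favour of A needs them to average (4.1 - 1.2)/(10/75), about 22 points, above.
- The sign alone flips at 1.2/(10/75) = 9 points, but the result is non-significant either way.

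**Reflux at 24 months (GERD-HRQL >16).** The bands sum to 49 + 14 + 1 = 64 of 65 in A and 55 + 10 + 0 = 65 of 66 in B, so one attender per arm is unclassified.
- A: 15 observed, up to 15 + 10 + 1 = 26 of 75.
- B: 10 observed, up to 10 + 9 + 1 = 20 of 75.
- One extreme is 26/75 (35%) v 10/75 (13%): chi-square = 150 × (26 × 65 - 10 × 49)²/(75 × 75 × 36 × 114) = 9.36, p = 0.002.
- The other is 15/75 (20%) v 20/75 (27%): chi-square = 150 × (15 × 55 - 20 × 60)²/(75 × 75 × 35 × 115) = 0.93, p = 0.33, in the opposite direction.

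**The case against.** The strongest reply is that retention is good (91% and 87%), losses are almost equal (8 v 6; 10 v 9), and no bias is demonstrated. That stands. So does the robustness of the 24-month %EWL result. What it does not answer is the absence of any stated method, or the sensitivity at 12 months.

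Four stronger readings are tempting and are not supported:

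- **That the trial is underpowered because 136 and 131 fall below the planned number.** Section 2.6 says "138 PATIENTS ARE REQUIRED TO BE 90% SURE", but for a binary non-inferiority outcome with no stated rate, so it is a weak benchmark for mean %EWL. If one assumes an SD of 20, which returns 138 for a continuous outcome, power is 90.2% at 138, 89.8% at 136 and 88.8% at 131. A binary rate of 95.8% gives 90.0%, 89.7% and 88.7%. The cost is about 0.4 and 1.4 points. The reduced numbers are already printed in both tables.
- **That reasons for loss were not reported.** Section 2.2 points to Figure 1, a flow diagram not shown in the available text. Reasons may be there.
- **That the narrowing between 12 and 24 months comes from the changing set of patients.** If the patients seen at 24 months are a subset of those seen at 12, explaining all of it would require the 2 lost from A to have averaged (67 × 63.7 - 65 × 62.8)/2, about 93, and the 3 lost from B (69 × 59.6 - 66 × 61.6)/3, about 16. Those values are implausible.
- **That a 9-point shift shows the 24-month result to be fragile.** It changes only the sign of a difference that is non-significant either way.

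Section 2.2 also excludes patients converted to open surgery, with no count given. Some absentees may be exclusions and not non-attenders. An analysis of all randomised patients as assigned would have to account for them too.

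**Conclusion.** The point holds as a limited one. The primary comparisons leave out 9.3% and 12.7% of randomised patients with no stated handling, although at least 9 of 14 and 14 of 19 have a usable 3-month weight. A reader might infer that the results are biased; the documents do not show that. The 24-month %EWL conclusion is robust. The 12-month one is not secure: from the printed summaries it is 4.1 points (95% CI about -0.4 to 8.6, p about 0.075), in conflict with the table's P<0.05, and a shift of about 4 points in A's 8 missing patients would decide significance. The 24-month reflux comparison is compatible with a clear excess in A or a small excess in B, but only at the extremes.

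This rests on reading the denominators as attender-only analysis, on patients seen at 3 months having been weighed, on a pooled t-test from rounded summaries, and, for the shifts, on a fixed SE and B's lost patients resembling B's attenders.

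**What to change.** - Analyse %EWL in all randomised patients as assigned, using a repeated-measures mixed model on the 3, 6, 12 and 24 month values, with arm, visit, arm-by-visit interaction and baseline BMI.
- Report the arm difference with a 95% CI at 12 and 24 months, and reconcile the 12-month p-value with the printed means and SDs.
- Add a shift analysis for the missing patients, judged on whether the conclusion changes and not on the sign of the difference.
- Give best/worst-case limits for 24-month GERD-HRQL >16 that include the unclassified attender in each arm: A 15-26/75, B 10-20/75.

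The cost is a little more analysis of data already collected, in software that fits mixed models. The model assumes that loss is explained by the observed weights, and the shift analysis tests that assumption.
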